4.4 Pharmacokinetic Per Protocol Set

All randomized study participants who are included in the SS, have no important protocol deviations (IPDs) that are considered to impact the study participant's data validity for analysis of the primary study objective, and have a sufficient number of bioanalytical assessments to calculate reliable estimates for the primary pharmacokinetic parameters for both treatments will be included in the Pharmacokinetic Per-Protocol Set (PK-PPS).

If a study participant's predose concentration is greater than 5% of the corresponding C_{max} value in both Dosing Periods, the study participant will be excluded from the PK-PPS. If this occurs in 1 of the 2 Dosing Periods, but not in the other Dosing Period, data of the other Dosing Period will be used. Furthermore, since the study participant will be entered as a random effect in the ANOVA, the data of the single Dosing Period can still be used for the bioequivalence assessment.

If vomiting occurs at or before 2 times of the median t_{max} of the study, the study participant will be excluded from the PK-PPS.

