Section 9.1 Definition of analysis sets	Revised text to state that study participants will be excluded from the PK-PPS if their predose concentrations are greater than 5% of the corresponding C_{max} value in both Dosing Periods, rather than in either Dosing Period.	Error correction.
Section 9.3.1 Pharmacokinetic analyses	Revised text to state that PK analyses will be performed on the SS and statistical analyses will be performed on the PK-PPS.	Clarification.
Section 9.5 Handling of protocol deviations	Added text to clarify that data will not yet be available at the time of the Data Evaluation Meeting to define the final PK-PPS, based upon the definition of PK-PPS provided in Section 9.1.	Clarification.
Section 9.8 Determination of sample size	Added text to clarify that a total of 19 participants will provide a power of 90% at the 5% significance level (one-sided) to declare BE.	Clarification
Section 10.2 Appendix 2: Clinical Laboratory Tests	Revised that clinical laboratory tests would be performed by a central laboratory to state that they will be performed by a local laboratory.	The single site for this study has a certified local clinical laboratory available.
Section 10.2 Appendix 2: Clinical Laboratory Tests	Added WBC count to the list of hematology parameters to be assessed.	Error correction.
Section 10.2 Appendix 2: Clinical Laboratory Tests	Revised that instead of a urine alcohol screen, an alcohol breath test would be performed.	Error correction.

SERIOUS ADVERSE EVENT REPORTING

Serious adverse event reporting (24h)	
[contact]
Email	[contact]

This document cannot be used to support any marketing application and any extensions or variations thereof.
PUBLIC COPY

TABLE OF CONTENTS

1	PROTOCOL SUMMARY	11
1.1	Synopsis	11
1.2	Schema	13
1.3	Schedule of Activities	15
2	INTRODUCTION	18
2.1	Study Rationale	19
2.2	Background	20
2.3	Benefit/Risk Assessment	20
2.3.1	Risk assessment for coronavirus disease 2019	21
3	OBJECTIVES AND ENDPOINTS	22
4	STUDY DESIGN	23
4.1	Overall design	23
4.2	Scientific rationale for study design	24
4.3	Justification for dose	24
4.4	End of study definition	24
5	STUDY POPULATION	24
5.1	Inclusion criteria	24
5.2	Exclusion criteria	25
5.3	Lifestyle restrictions	26
5.3.1	Meals and dietary restrictions	26
5.3.2	Caffeine, alcohol, and tobacco	26
5.3.3	Activity	27
5.3.4	Food intake times	27
5.3.5	Other restrictions	27
5.4	Screen failures	27
6	STUDY TREATMENTS	28
6.1	Treatments administered	28

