Study participants will be closely monitored for any signs and symptoms of COVID-19 (eg, fever, dysgeusia [taste loss/change], dysosmia [loss or distortion/change of smell], persistent cough, and dyspnea) throughout the study. If symptoms and/or clinical signs of infection are identified, the Investigator will decide whether these findings will be handled as suspected or confirmed COVID-19. The use of testing for SARS-CoV-2 will be determined by reference to the regulatory and healthcare guidance in place locally at the time. In the case that COVID-19 is suspected or confirmed, administration of further IMP to that study participant will be suspended, and the Investigator will determine (ideally in discussion with the UCB Study Physician) how soon the study participant may be discharged from the study site, and whether this will be to their home or another healthcare facility.

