7.2 Study participant discontinuation/withdrawal from the study

Study participants are free to withdraw from the study at any time, without prejudice to their continued care.

A study participant may withdraw from the study at any time at his own request, or may be withdrawn at any time at the discretion of the Investigator for safety, behavioral, compliance, or administrative reasons.

If the study participant withdraws consent for disclosure of future information, the Sponsor may retain and continue to use any data collected before such a withdrawal of consent.

If a study participant withdraws from the study, he may request destruction of any samples taken and not tested, and the Investigator must document this in the site study records.

See the Schedule of Activities (Section 1.3) for data to be collected at the time of study discontinuation and follow up and for any further evaluations that need to be completed.

Study participants should be withdrawn from the study if any of the following events occur:

1. Study participant withdraws his consent.
2. Study participant develops an illness that would interfere with his continued participation.
3. Study participant is noncompliant with the study procedures in the opinion of the Investigator.
4. Study participant takes prohibited concomitant medications as defined in this protocol.
5. The Sponsor or a regulatory agency requests withdrawal of the study participant.

Participants must be withdrawn by the Investigator based on discussion with the Sponsor and Medical Monitor under the following circumstance:

Any confirmed COVID-19 case that warrants discontinuation in the judgment of the Investigator or Sponsor to protect the safety of the participant, other participants, or study site staff (see Section 2.3.1 for further details).

Study participants who discontinue the study early for reasons other than IMP-related safety may be replaced upon agreement with the Investigator and Sponsor. Replacement study participants will receive the same treatment sequence that was assigned to the study participant who dropped out.

Investigators should contact the Medical Monitor, whenever possible, to discuss the withdrawal of a study participant in advance.

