5.1.1.7 Handling of dropouts or missing data

Missing data will not be imputed unless otherwise stated. Data from subjects who prematurely discontinue the study will be used to the maximum possible extent.

Partial dates for concomitant medication and AEs will be imputed as described in Section 6.3 and Section 10.2.

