11.1.2 Protocol deviations

All protocol deviations will be reviewed on an ongoing basis as part of the data cleaning and evaluation process. After all data have been verified/entered into the database, and prior to database lock, a Data Evaluation Meeting (DEM) will be performed. The purpose of this review meeting will be to examine all protocol deviations, define the PK-PPS, and to verify the quality of the data. If PK parameters are needed to define PK-PPS, it will be performed based on the ADPP (Pharmacokinetic Parameters Analysis Data). The data evaluation will also help in guiding decisions on how to manage data issues on a case-by-case basis (e.g., missing values, dropouts, and protocol deviations).

Important Protocol Deviations (IPDs) that are considered to impact the study participant's data validity for analysis of the primary study objective will be identified and classified by the deviation types listed in the PD specification document.

Accepted deviations from theoretical time points will be described in the appropriate documents and included in the electronic Trial Master File. After the data review, resolution of all issues, and documentation of all decisions, the database will be locked.

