11.4 Appendix 4: PK parameter calculations

Pharmacokinetic parameters will be calculated by non-compartmental analysis methods from the concentration-time data following these guidelines:

- Actual time will be used in the calculation of all derived pharmacokinetic parameters.
- There will be no imputation of missing data.
- BLQ values at the beginning of a subject profile (i.e., before the first incidence of a measurable concentration) will be assigned to zero. Embedded BLQ values (i.e., occurring between two measurable data points) and BLQ values occurring post- C_{max} will be considered missing.

Pharmacokinetic parameters will be estimated according to the guidelines presented in [Table 11-1](#).

Table 11-1: Pharmacokinetic Parameter and Estimation

Parameter	Guideline for Derivation
C_{max} and t_{max}	Obtained directly from the observed concentration-time data
C_{last}	Last observed (quantifiable) concentration, obtained directly from the observed concentration versus time curve

Parameter	Guideline for Derivation
AUC _(0-t)	
The AUC from zero time (pre-dose) to the time of last quantifiable concentration (AUC_(0-t)) will be calculated by a combination of linear and logarithmic trapezoidal methods. Unless specifically requested and justified the linear up/log down trapezoidal method will be employed.
 
The AUC_(0-t) is the sum of areas up to the time of the last quantifiable sample:
 $AUC_{(0-t)} = \int_0^t C(t) dt$
AUC	
The area from zero time extrapolated to infinite time will be calculated as follows:
 $AUC = AUC_{(0-t)} + \frac{C_{last}}{\lambda_z}$ 
where C_{last} is the last observed quantifiable concentration.

AUC _{extr}	
The percentage of AUC obtained by extrapolation will be calculated as follows:
 $AUC_{extr} = \frac{AUC - AUC_{(0-t)}}{AUC} \times 100$ 
Unless otherwise determined by PK Scientist's best knowledge and judgment, if the AUC_{extr} is greater than 20%, AUC_{extr} and all dependent parameters (i.e., AUC, MRT, V_Z/F and CL/F) will be flagged in listings and excluded from summary tables and statistical analysis of PK parameters. The reason for flagging/exclusion will be footnoted in parameter listings.

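### Does the PK per-protocol set need a numeric sample-completeness rule for Cmax and AUC(0-t)?

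*SAP*

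**What the plan says.** SAP 4.4, repeated in SAP 9.2.1 and Protocol 9.1, sets three conditions for the PK-PPS: membership of the Safety Set, no important deviation that affects the validity of the primary analysis, and adequate PK data. On the last, participants with a "sufficient number of bioanalytical assessments to calculate reliable estimates for the primary pharmacokinetic parameters for both treatments will be included". Separate explicit rules cover predose carry-over and early vomiting.

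SAP 11.4 sums AUC(0-t) to the last quantifiable sample and adds "There will be no imputation of missing data". For the extrapolated quantities it has a 20% limit: above it, "AUC_{extr} and all dependent parameters (i.e., AUC, MRT, V_Z/F and CL/F) will be flagged in listings and excluded from summary tables". That sentence opens with a clause that lets the PK scientist decide otherwise. AUC(0-t) and Cmax are not on the list.

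On incomplete participants, SAP 5.1.1.7 states "Data from subjects who prematurely discontinue the study will be used to the maximum possible extent". SAP 11.1.2 has the Data Evaluation Meeting guide decisions on a "case-by-case basis (e.g., missing values, dropouts, and protocol deviations"), before database lock. It allows the PK parameter dataset to be used if the set cannot be defined without it. SAP 9 assigns PK analyses to the Safety Set and statistical analyses to the PK-PPS.

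**The concern.** A secondary parameter has a numeric default and the co-primary has none, although AUC(0-t) is the quantity that loses area directly when sampling ends early. Early ends are foreseeable: for suspected COVID-19, Protocol 2.3.1 has the investigator decide "how soon the study participant may be discharged from the study site".

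Two other features add to the worry. The instruction to use discontinued participants' data as fully as possible seems to pull against the need for both treatments. Protocol 7.2, under which early leavers "may be replaced upon agreement with the Investigator and Sponsor", does not say whether the replaced participant's single period enters the model. In addition, the trial is open-label and PK parameters may be consulted when the set is defined, so a keep-or-drop decision could be made with the primary values in view. If a truncated reference profile were kept and the true ratio lay at 0.80, the chance of wrongly declaring equivalence on AUC(0-t) would exceed 5%.

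**Working it through.** **1. The plan's own figures.** Inputs from Protocol 9.8 and SAP 3: CV 20%, one-sided 5%, limits 0.80 to 1.25. For two one-sided tests in a 2×2 crossover, s = √ln(1+CV²) = √ln(1.04) = 0.198, SE = s√(2/N) and df = N−2. Power is 90.7% at N = 19, ratio 1.00. At N = 24 it is 89.6% (ratio 0.95) and 90.3% (ratio 1.05). The stated 90% is reproduced.

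**2. How short is a truncated AUC(0-t)?** Inputs from Protocol 2: one compartment, half-life 9 h, tmax 1 h, volume 0.5 L/kg. Assumed: body weight 62.5 kg and complete absorption. Then k = ln2/9 = 0.077/h, ka = 4.036/h (solved for tmax 1 h) and C0 = 50 mg/(0.5 × 62.5 L) = 1600 ng/mL. At 48 h, C = 1600 × 1.019 × e^(−0.077×48) ≈ 40 ng/mL, against an LLOQ of 2 ng/mL (Protocol 8.1). An early last time therefore means missed samples, not values below the LLOQ.

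The extrapolated fraction is [ka/(ka−k)]·e^(−kt), and AUC(0-t)/AUC(0-48 h) = (1−extr at t)/(1−extr at 48 h). On the SAP sampling grid with linear-up/log-down:

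| Last sample | AUCextr | AUC(0-t)/AUC(0-48 h) | Same ratio at half-life 7 h; 11 h |
|---|---|---|---|
| 36 h | 6.4% | 0.960 | 0.980; 0.941 |
| 24 h | 16.1% | 0.861 | 0.913; 0.816 |
| 16 h | 29.8% | 0.720 | 0.796; 0.662 |
| 12 h | 40.5% | 0.610 | 0.693; 0.550 |

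At 9 h, the 20% default catches profiles ending at 16 h or earlier, not one ending at 24 h. Interior gaps matter little. A missing 36 h sample changes nothing, missing 0.75 to 1.25 h lowers Cmax by 2–3%, and missing all of 0.25 to 1.5 h lowers it by 5–7%.

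**3. Effect on the ratio.** One truncated period among 24 participants multiplies the ratio by f^(1/24). For 24 h, 0.861^(1/24) = 0.994; for 16 h, 0.720^(1/24) = 0.986.

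**4. Effect on the AUC(0-t) verdict.** The documents give an AUC CV of 4% to 12%, median 6%. Pass rates from 40,000 simulated trials per setting, test period truncated:

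| CV, true ratio | Profiles cut | Kept | Dropped |
|---|---|---|---|
| 6%, 0.95 | one, 24 h or 16 h | 100% | 100% |
| 12%, 0.95 | one, 24 h | 99.9% | 99.9% |
| 12%, 0.95 | one, 16 h | 99.6% | 99.9% |
| 12%, 0.95 | four, 16 h | 88.6% | 99.7% |
| 12%, 0.90 | one, 24 h | 92.7% | 94.3% |
| 12%, 0.90 | one, 16 h | 87.3% | 94.5% |

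**5. Type I error at a true ratio of exactly 0.80.** 400,000 trials, one profile kept:

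| CV | Cut at | Reference cut | Test cut | Average |
|---|---|---|---|---|
| 6% | 24 h | 8.1% | 1.8% | 5.0% |
| 6% | 16 h | 9.4% | 0.3% | 4.8% |
| 12% | 24 h | 6.8% | 3.2% | 5.0% |
| 12% | 16 h | 8.3% | 1.6% | 5.0% |

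There is no inflation on average if the cut falls equally often on either formulation.

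**6. Cost of dropping.** Cmax power at CV 20%, ratio 0.95 goes from 89.6% (24) to 88.3% (23). Keeping a one-period dropout beside 23 pairs would lower the variance of the log ratio by only 0.6–1.4%.

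**7. Reading the passages together.** SAP 4.4 requires reliable estimates of both primary parameters in both treatments. A one-period participant, replaced or not, is therefore outside the primary model. SAP 9.2.1 still lists that participant's parameters, which fits the maximum-use sentence in SAP 5.1.1.7. The single-period exception for predose carry-over stands directly after the general rule. Collection times are recorded as samples are drawn (Protocol 8.1), so completeness can be judged before any concentration is known. The protocol's summary of changes for Section 9.5, read for intent only, says "data will not yet be available at the time of the Data Evaluation Meeting to define the final PK-PPS".

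**The case for a change.** The best case for a change is that the SAP exists to remove such choices. A missing criterion for a co-primary endpoint, in an open-label trial where PK parameters may be consulted to define the set, leaves room for a decision coloured by the result. The direction of error depends on which formulation was cut, and that is known. If reference profiles were kept and test profiles dropped, the type I error would not average out. The remedy would be a few sentences with no new data.

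Part of this stands. No number is written down, and a 24 h profile is a real grey area: about 14% short, yet unflagged by the 20% default. The plan permits sight of PK values when the set is defined, though it does not require it. With several cut profiles, or a true ratio near 0.90 at CV 12%, the choice would be felt.

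Other parts do not stand. Secondary AUC is not removed by a hard rule, since the PK scientist may override it; the contrast is between a default and no default. The dropout passages do not conflict. The inflated error needs three things together: a true ratio at the limit, a truncated reference period, and its retention despite the reliability condition. Participants are confined for 48 h, so truncation needs an unusual event. In Period 1, suspected COVID-19 also suspends further dosing, which would probably remove the participant for want of a second treatment. The deviation specification named in SAP 11.1.2 is not public and may already hold a completeness rule.

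**Conclusion.** No change is needed. The plan lacks a number, but it has a governing principle that analysts can apply sensibly: both primary parameters must be reliably estimated in both periods. An AUC(0-t) 28% or more below its 48 h value does not meet that test on any ordinary reading. Milder truncation is left to judgement, but one kept 24 h profile shifts the ratio by 0.6% and leaves the AUC(0-t) pass rate at about 99.9% at CV 12% and ratio 0.95. Dropping the participant instead costs 1.3 points of Cmax power (89.6% to 88.3%).

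This rests on a half-life near 9 h (7 to 11 h examined), an AUC CV of at most 12%, one or two truncated profiles at most, and a true ratio not close to 0.80 or 1.25. The sponsor could record a completeness threshold before bioanalysis as good housekeeping, but a sound conclusion is expected from the plan as written.

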5 STATISTICAL ANALYSES

5.1 General Considerations

Statistical evaluation will be performed by the Sponsor or designee and supervised by the Exploratory Statistics Department of UCB. Statistical analysis and generation of tables, figures, and study participant data listings will be performed using SAS Version 9.3 or higher. The PK noncompartmental analysis (NCA) will be performed using Phoenix WinNonlin® Version 8.2 or higher (Certara L.P., Princeton, NJ, USA) for Pharmacokinetics parameters estimation.

A complete set of listings containing both all documented data and all calculated data will be generated by treatment sequence, unless otherwise specified. Missing data will not be imputed, unless otherwise specified. Outlier detection and statistical analysis of outliers will not be performed.

Descriptive statistics will be displayed to provide an overview of the study results. For categorical endpoints, the number and percentage of study participants in each category will be presented. The denominator for percentages will be based on the number of study participants appropriate for the purpose of the analysis. For continuous endpoints, descriptive statistics will include number of study participants, mean, standard deviation, median, minimum, and maximum. The descriptive statistics for plasma concentrations and PK parameters will be described in Section 9.1 and Section 9.2.1.

Unless otherwise noted, the denominator for percentages should be based on the number of participants included in the respective analysis set. For summaries of demographics and Baseline characteristics: summarize percentages based on all participants in the analysis set and include a potential “Missing” category (corresponding to participants with missing data at the time of the variable being summarized) as the last row in the list of categories being summarized.

Percentages will be presented to 1 decimal place. If the percentage is 100%, do not present a decimal. If the percentage is 0, do not present the percentage. Typically, the % sign should be presented in the column header, but not with each individual value.

Decimal places for descriptive statistics will always apply the following rules, unless otherwise stated:

- “n” will be an integer
- Mean, SD, and median will use one additional decimal place compared to the original data
- CV [%] will be presented with one decimal place
- Minimum and maximum will have the same number of decimal places as the original value

Derived variables in general will display the mean, SD and median to 1 more decimal place than the variables used in the derivation. If the number of decimal places reported in the raw data is varied then use either the maximum raw number of reported decimal places or 3, whichever is the lowest, as a guide for the descriptive statistics.

If participants have more than one observation for a given time point, the observation closest to the intended time point will be used. If both observations are equidistant from the intended time point, then the later value will be used.

Refer to Appendix 3 (Section 11.3.1 and Section 11.3.2) for standard reporting procedures of PK concentrations and parameters in listings, tables, and figures.

5.1.1 General study level definitions

5.1.1.1 Analysis Time Points

5.1.1.1.1 Relative day

Relative day will be derived with the date of IMP administration in each Dosing Period as reference for that specific Dosing Period.

For days on the day of IMP administration in each Dosing Period

Relative day will be calculated as follows:

Relative day = Current date - Date of IMP administration + 1
i.e., the day of IMP administration in each Dosing Period will have a relative day of '1'.

For days prior to IMP administration in each Dosing Period

Relative day will be prefixed with '-' and calculated as follows:

Relative day = Current date - Date of IMP administration within the same Dosing Period
e.g., the day prior to the IMP administration will have a relative day of '-1'.

For days prior to the first IMP administration in the Screening Period

Relative day will be prefixed with '-' and calculated as follows:

Relative day = Current date - Date of first IMP administration
e.g., Screening Visit that is 7 days prior to the first IMP administration will have a relative day of '-7'.

For days after the day of IMP administration in Dosing Period

Relative day will be prefixed with '+' and will be calculated as follows:

Relative day = Current date - Date of IMP administration within the same Dosing Period
e.g., the day after IMP administration in a Dosing Period will have a relative day of '+1'.

For days after the Dosing Period

Relative day will be prefixed with '+' and calculated as follows:

Relative day = Current date - Date of last IMP administration
e.g., A certain day in a washout period following Dosing Period 1 that is 7 days after IMP administration in Dosing Period 1 will have a relative day of '+7'.
e.g., Safety Follow-Up Visit that is 8 days after the last IMP administration will have a relative day of '+8'.

Relative day will not be calculated for partial dates. Relative day for partial days will be displayed as '--' to distinguish it from missing values which are displayed as blanks.

